5.2 Initiation of a new cycle of pracinostat and ruxolitinib

A new course of pracinostat may begin on the scheduled Day 1 of a new cycle if:

- The ANC is $\geq 0.5 \times 10^9/L$
- The platelet count is $> 25 \times 10^9/L$,
- Any drug-related grade 3-4 adverse event that may have occurred has resolved to \leq grade 1 severity or baseline
- Normal potassium and magnesium serum levels (hypokalemia or hypomagnesemia should be corrected prior to pracinostat administration)
- QTcF interval < 500 msec (reversible causes of QTc prolongation should be corrected, e.g. hypomagnesemia and hypokalemia, and ECG repeated. Provided that the patient is asymptomatic and that QTc decreases below 500 msec, pracinostat administration may continue).

If these conditions are not met on Day 1 of a new cycle, the subject will continue ruxolitinib alone (see guidelines for restarting/continuing ruxolitinib in the next paragraph) and be evaluated weekly and a new cycle of pracinostat will not be initiated until the toxicity has resolved as described above. If pracinostat dosing was interrupted during the previous cycle or if the new cycle is delayed due to toxicity newly encountered on the scheduled Day 1, then the new cycle of pracinostat will be started when the criteria above are met AND with at least a one-level dose reduction.

Treatment with ruxolitinib may restart/continue at 5mg QD so long as $ANC > 0.5 \times 10^9/L$ AND platelets $> 25 \times 10^9/L$ (with approval of Principal Investigator, and documented) or at 5mg BID so long as $ANC \geq 1 \times 10^9/L$ AND platelets $> 50 \times 10^9/L$ while waiting to initiate a new cycle of pracinostat. If the toxicity has not resolved as described above within 8 weeks of the scheduled start date for the new cycle of pracinostat, the patient may discontinue treatment with pracinostat and continue therapy with ruxolitinib alone. In unusual circumstances this rule may be modified by the Principal Investigator if felt to be in the best interest of the patient (for example, responding patient with neutropenia or low platelets, that resolve past 8 weeks may be restarted on therapy); such case must be fully documented.

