4.0 PATIENT ELIGIBILITY CRITERIA

Inclusion criteria

1. Diagnosis of MF (either primary or post essential thrombocythemia/polycythemia vera) requiring therapy, including those previously treated and relapsed or refractory, or if newly diagnosed, with intermediate-1 or -2 or high risk according to International Prognostic Scoring System (IPSS).
2. Palpable splenomegaly of more than or equal to 5 cm below left costal margin on physical exam
3. Understanding and voluntary signing an IRB-approved informed consent form.
4. Age \geq 18 years at the time of signing the informed consent.
5. Disease-free of other malignancies.
6. ECOG performance status 0 to 2.

7. Negative pregnancy test in females of childbearing potential (FCBP)[†] Male patients with female partners of child-bearing potential and female patients of childbearing potential are required to use two forms of acceptable contraception, including one barrier method, during their participation in the study and for 30 days following last dose. Acceptable forms of contraception include 1 highly effective method such as an intrauterine device (IUD), hormonal (birth control pills, injections, or implants), tubal ligation, or partner's vasectomy and at least 1 additional approved barrier method such as a latex condom, diaphragm, or cervical cap. Female patients of childbearing potential must not be breast-feeding or planning to breast feed and must have a negative pregnancy test \leq 7 days before first study treatment.
8. QTcF interval \leq 470 msec
9. Normal serum potassium and magnesium levels
10. Adequate organ function as demonstrated by the following:
 - Direct bilirubin \leq 2.0 mg/dL
 - Serum creatinine \leq 2.0 mg/dL.
 - SGPT \leq 3 x upper limit of normal (unless considered to be related to MF or patient has known history of Gilberts)
11. Platelets $>/= 50 \times 10^9/L$
12. ANC $>/= 1 \times 10^9/L$

Exclusion Criteria

1. Prior therapy with a JAK inhibitor (other than ruxolitinib for less than 3 months duration and currently on it) or HDACi. Patients that are currently on ruxolitinib for less than 3 months of therapy are eligible.
2. Use of any other standard or experimental therapy within 14 days of starting study therapy.
3. Lack of recovery from all toxicity from previous therapy to grade 1 or baseline.
4. Suspected pregnancy, pregnant or lactating females.

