5.5 Pretreatment Evaluation

- History and physical exam including vital signs, body weight and height, and spleen and liver measurements. This also includes a transfusion history for 3 months prior to day 1 and concomitant medication notation (within 14 days of study day 1)
- CBC and differential, electrolytes (Na, K, Cl, Mg, HCO3), creatinine, uric acid, BUN, glucose, total and direct bilirubin, and SGPT, PT/PTT, INR (within 14 days of study day 1).
- Bone marrow biopsy and aspirate (within 1 month of study day 1, or within 3 months of study day 1 if patient was not on any therapy).
- ECG (within 14 days of study day 1)
- Pregnancy test (for FCBP only) within 7 days of study day 1
- Myeloproliferative Neoplasm Symptom Assessment Form Total Symptom Score (MPN-SAF TSS) questionnaire

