5.6 Evaluation During Study

- Directed history and physical examination including vital signs, body weight, and spleen and liver measurements once each cycle on cycles 2-7, then once every 3 cycles (C10, C13, C16, ...). This also includes a transfusion history for previous cycle of therapy and concomitant medication notation. Spleen and liver measurements will be obtained by the physicians or physician assistants during the clinic visit and documented in the medical record.
- CBC and differential, electrolytes (Na, K, Cl, Mg, HCO3), creatinine, BUN, glucose, total bilirubin, and SGPT every 2 weeks for 6 cycles, then CBC with differential every cycle and electrolytes (Na, K, Cl, Mg, HCO3), creatinine, BUN, glucose, total bilirubin, and SGPT every 3 cycles and as deemed appropriate while on therapy. Therapy also includes the first 3 months of ruxolitinib alone.
- ECG will be performed prior to the first cycle of pracinostat (C4), then once during cycles 5 and 6, then every 3 cycles starting with cycle 10 (specifically, ECG should be performed approximately 90 minutes post pracinostat dosing on the day of visit to MD Anderson)
- Bone marrow aspiration and biopsy after cycles 6 (+/- 10 days) and 12 (+/- 10 days), and if deemed appropriate by the investigator, every 6 cycles after cycle 12.
- Response assessment after cycle 3 and cycle 6, then every 6 cycles. Assessment may not include bone marrow biopsy on all occasions.
- Collect any unused study drug and review patient study drug dosing diary for compliance during each cycle for the first 7 cycles then every 3 cycles.
- Continuous assessment of AEs
- Myeloproliferative Neoplasm Symptom Assessment Form Total Symptom Score (MPN-SAF TSS) questionnaire during each cycle for the first 7 cycles then every 3 cycles.

Every effort will be made to adhere to the schedule of events and all protocol requirements within the +/- 10 day window. Variations in schedule of events and other protocol requirements that do not affect the rights and safety of the patient will not be considered as deviations. Such variations may include laboratory assessments completed outside of schedule, occasional missed required research samples such as PK or PD. All dose adjustments will be made according to the protocol unless discussed with the PI and do not exceed the dosages described in the protocol.

Outside Physician Participation During Treatment

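### The first pracinostat dose is held to a QTcF limit of 500 msec, not to the 470 msec limit applied at screening

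*Combined protocol and SAP*

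**What the plan says.** - **Entry limit.** Section 4.0, inclusion 8: "QTcF interval \leq 470 msec". Section 3.2, under QTc prolongation, reports asymptomatic prolongation in pracinostat trials and, in the next sentence, excludes patients whose QTc is prolonged at screening.
- **When it is read.** Section 5.5: "ECG (within 14 days of study day 1").
- **When pracinostat starts.** Section 5.0 gives ruxolitinib alone for three 28-day cycles and adds pracinostat at cycle 4. Ruxolitinib taken before enrollment counts toward the three cycles.
- **ECG before the first dose.** Section 5.6: "ECG will be performed prior to the first cycle of pracinostat (C4"). The schedule attaches no limit to this reading.
- **Limit for starting a course.** Section 5.2: "QTcF interval < 500 msec (reversible causes of QTc prolongation should be corrected". The list covers any new course and has no separate rule for the first one. The QTc bullet ends by speaking of continuing the drug.
- **Companion entry criterion.** Inclusion 9, "Normal serum potassium and magnesium levels", is carried into Section 5.2: "Normal potassium and magnesium serum levels (hypokalemia or hypomagnesemia should be corrected prior to pracinostat administration").

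**The concern.** The protocol's own text ties the 470 msec limit to pracinostat exposure. In a ruxolitinib-naive patient that exposure begins three cycles after the limit was checked. QTc may change in the meantime, and the Section 5.3 ban on QT-prolonging drugs applies only to courses that include pracinostat, so such drugs are not prohibited during the lead-in.

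The pre-C4 ECG would detect a change, but it is judged against the looser figure. A looser limit is easy to defend for a patient who has already taken the drug and is being followed on it. The documents give no reason for applying it to a patient about to take the first dose. At stake is whether the entry safeguard still works when the exposure it was written for begins.

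**Working it through.** The plan states no figure to reproduce. The check sets the two limits side by side and adds simple arithmetic on timing.

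**1. What each QTcF band leads to**

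| QTcF | At screening (4.0) | On the pre-C4 ECG (5.2) |
|---|---|---|
| 470 msec or less | eligible | may start |
| above 470, below 500 | not eligible | may start |
| 500 or more | not eligible | not started; correct causes, repeat ECG |

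The limits disagree only in the middle row. Width: 500 − 470 = 30 msec. A patient who meets the entry limit has at least 30 msec of room below 500; a patient in the band has less.

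**2. Dose in the band.** Exclusion 1 bars prior HDAC inhibitors, so this is first exposure. The one-level reduction in Section 5.2 needs either an interruption in the previous pracinostat cycle or a delay for toxicity newly found on Day 1. A reading below 500 passes the criterion and causes neither, so the dose is Level 0. The 60 mg comes from the dose-level table in Section 5.1; Section 5.0 names no starting dose.

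**3. Time from the screening ECG to the first pracinostat dose**

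- Ruxolitinib-naive, nominal: 3 × 28 = 84 days; 84 + 14 = up to 98 days.
- If the visit window in Section 5.6 ("all protocol requirements within the +/- 10 day window") is also used: 98 + 10 = 108 days.
- With one maximum 8-week delay allowed by Section 5.0: 98 + 56 = 154 days.
- With nearly full credit for earlier ruxolitinib: about 0 + 14 = 14 days.

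The limit a patient has shown close to the first dose thus depends on ruxolitinib history. A patient with nearly full credit has met 470 within about two weeks; a naive patient need only show less than 500. Both face the same Section 5.2 limit on the pre-C4 ECG.

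**4. Whether another rule closes the gap**

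- Potassium and magnesium must be normal at cycle start and are monitored: "electrolytes (Na, K, Cl, Mg, HCO3), creatinine, BUN, glucose, total bilirubin, and SGPT every 2 weeks for 6 cycles".
- QT-prolonging drugs are banned during pracinostat courses, including the first, and concomitant drugs are reviewed (Section 5.3).
- A family history of long QT syndrome is excluded (Section 4.0).
- Section 5.2 permits a course to begin and does not compel it; Section 5.1 allows other dose changes with the Principal Investigator's approval.

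Each lowers the chance of harm. None sets a QTcF limit below 500 msec for the first dose.

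**The case against.** The strongest reply is that this is a deliberate choice. The authors carried the potassium and magnesium criterion forward and, in the next bullet, wrote a different QTcF figure. Platelets (at least 50 at entry, above 25 at cycle start, × 10⁹/L) and neutrophils (at least 1, then at least 0.5) loosen in the same way. Stricter entry than cycle-start limits may simply be this protocol's pattern. The reversible routes into the band are largely covered, only asymptomatic prolongation is reported, and the pracinostat QTc data that might justify either figure would be in the Investigator's Brochure, which is not available here.

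Much of this stands. It shows that the plan is not in error and that the risk may be small. It does not supply a reason for the first dose. The protocol expects ruxolitinib to lower blood counts, which explains the looser count limits; it describes no expected QTc change in the lead-in.

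A reader might also infer more than the text supports:

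- **That Sections 3.2 and 5.2 contradict each other.** They do not; Section 3.2 speaks of screening.
- **That the first dose rests on a stale ECG.** It does not; a current ECG is required before cycle 4. The interval shows how early the 470 limit is applied, not how old the last reading is.
- **That 98 or 108 days is the maximum.** Section 5.0 allows delays of up to 8 weeks.
- **That the added hazard can be sized.** The documents give neither the size of pracinostat's QTc effect nor the number of patients in the band.

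**Conclusion.** The point holds as a gap in design, and closing it is a cheap improvement. The 470 msec limit is applied at screening only, and a patient with no pracinostat exposure and a QTcF above 470 and below 500 msec may start at Level 0. The affected band is 30 msec wide. The added risk in it and the number of patients concerned are unknown.

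This rests on two readings: that the Section 5.2 criteria govern C4D1, and that Level 0 is the starting dose. If Section 5.2 were taken to cover later cycles only, the first dose would have no numeric QTcF limit and the gap would be wider. The 500 msec limit for later cycles, the platelet and neutrophil limits, and the ECG schedule after the first dose are not in question.

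**What to change.** Add to Section 5.2:

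> Before the first pracinostat dose (C4D1), QTcF must be ≤470 msec on the pre-C4 ECG or on a repeat after reversible causes are corrected. Until then the patient continues ruxolitinib alone and is re-evaluated weekly under the existing Section 5.2 rules. A delay for QTcF >470 and <500 msec does not by itself trigger the one-level dose reduction.

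Keep 500 msec for later cycles. Add no waiver that lets a patient still above 470 msec start. The Principal Investigator exception in Section 5.2 modifies the 8-week rule and should not be stretched to cover an unmet start criterion. If the sponsor does intend 500 msec for first exposure, the protocol should say so and give the reason.

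**Cost.** The change uses an ECG the protocol already requires. Repeat ECGs fall only on patients above 470 msec, at most 8 each if done weekly over 8 weeks. The real downside is for efficacy. Under Section 8.0 a patient who starts pracinostat late or never stays in the response-rate denominator, at 1/25 = 4 percentage points each. If cycles are counted by calendar, a full 8-week delay leaves 84 − 56 = 28 days of combination therapy before the assessment at the end of cycle 6.

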5.3 Concomitant Therapy

Supportive measures consistent with optimal patient care may be given throughout the study. Concomitant medications will be captured in the medical record and will not be recorded on the case report form.

- Therapies considered necessary for the patient's well-being may be administered at the discretion of the investigator. These therapies include, but are not limited to antibiotics, analgesics, antihistamines, or other medications. Guidance for growth factors and transfusions of red blood cells, platelets, or fresh frozen plasma are described below:
- Packed red blood cells (RBCs): Transfusions of 2 units of packed RBCs should be considered for a decline in hemoglobin to <8 g/dl or symptoms of cardiovascular compromise. The following transfusion thresholds and guidelines are recommended for study participants:
 - hemoglobin <8 g/dl, 2 units of packed RBCs; hemoglobin <7, three units of packed RBCs
 - Platelets: Six to 10 units of random donor platelets or one cytopheresis unit of single donor platelets should be administered to all subjects with signs of hemostatic failure (i.e., bleeding or petechiae) or life-threatening thrombocytopenia (i.e., platelet count < 10,000/ μ L)
 - Growth factor use with epoetin, darbepoetin, or granulocyte colony-stimulating factor must be terminated at least 14 days before initiation of study treatment and may not be used as part of supportive therapy while the patient is on study, except if in patients' best interest after approval of PI (e.g. neutropenic fever)
 - Patients should not receive androgens or steroids for treatment of their anemia or thrombocytopenia as part of supportive therapy
 - Patients may receive hydrocortisone prophylactically to prevent transfusion reactions but chronic systemic steroid (above 5mg/day) are not allowed.
- Over-the-counter products such as herbal preparations or dietary supplements with the exception of multivitamins, Ensure, and similar nutritional supplements are not allowed throughout the trial. Patients should stop using these herbal medications at least 7 days prior to the first dose of study medication.

Prohibited medications

Drug interaction studies with pracinostat are ongoing. Medications that have possible risk of prolonging the QT interval and/or Torsades de Pointes (listed below) may have an unacceptable risk of co-administration with pracinostat and are prohibited during courses in which pracinostat is administered. The following website was used as a guide: <http://www.qtdrugs.org/medical-pros/drug-lists/drug-lists.htm#>. All concomitant medications that the subject is receiving both prior to enrollment and during study

conduct must be carefully reviewed and monitored. Subjects should avoid grapefruit juice and Seville oranges.

Prohibited drugs: Drugs that Have a Risk of Prolonging the QT Interval and/or Inducing Torsades de Pointes

Albuterol (salbutamol)
Alfuzosin
Amantadine
Amiodarone
Amisulpride
Amitriptyline
Amoxapine
Amphetamine
Anagrelide
Apomorphine
Arformoterol
Aripiprazole
Arsenic trioxide
Astemizole (Off US mkt)
Atazanavir
Atomoxetine
Azithromycin
Bedaquiline
Bepridil (Off US mkt)
Bortezomib
Bosutinib
Chloral hydrate
Chloroquine
Chlorpromazine
Ciprofloxacin
Cisapride (Off US mkt)
Citalopram
Clarithromycin
Clomipramine
Clozapine
Cocaine
Crizotinib
Dabrafenib
Dasatinib
Desipramine
Dexmedetomidine
Dexmethylphenidate
Dextroamphetamine (d-Amphetamine)
Dihydroartemisinin+piperaquine
Diphenhydramine (doses up to 25 mg per day allowed)
Disopyramide
Dobutamine
Dofetilide
Dolasetron

Domperidone
Dopamine
Doxepin
Dronedarone
Droperidol
Ephedrine
Epinephrine (Adrenaline)
Eribulin
Erythromycin
Escitalopram
Famotidine
Felbamate
Fenfluramine
Fingolimod
Flecainide
Fluconazole
Fluoxetine
Formoterol
Foscarnet
Fosphenytoin
Eurosemide (Furosemide)
Galantamine
Gatifloxacin
Gemifloxacin
Granisetron
Grepafloxacin
Halofantrine
Haloperidol
Hydrochlorothiazide
Ibutilide
Iloperidone
Imipramine (melipramine)
Indapamide
Isoproterenol
Isradipine
Itraconazole
Ivabradine
Ketoconazole
Lapatinib
Levalbuterol (levsalbutamol)
Levofloxacin
Levomethadyl
Lisdexamfetamine
Lithium
Mesoridazine

Metaproterenol
Methadone
Methamphetamine (methamphetamine)
Methylphenidate
Metronidazole
Midodrine
Mifepristone
Mirabegron
Mirtazapine
Moexipril/HCTZ
Moxifloxacin
Nelfinavir
Nicardipine
Nilotinib
Norepinephrine (noradrenaline)
Norfloxacin
Nortriptyline
Ofloxacin
Olanzapine
Ondansetron
Oxytocin
Paliperidone
Pantoprazole
Paroxetine
Pasireotide
Pazopanib
Pentamidine
Perflutren lipid microspheres
Phentermine
Phenylephrine
Phenylpropanolamine
Pimozide
Pipamperone
Posaconazole
Probucol
Procainamide
Promethazine
Protriptyline
Pseudoephedrine
Quetiapine
Quinidine
Quinine sulfate
Ranolazine
Rilpivirine
Risperidone

Ritodrine
Ritonavir
Roxithromycin
Salmeterol
Saquinavir
Sertindole
Sertraline
Sevoflurane
Sibutramine
Solifenacin
Sorafenib
Sotalol
Sparfloxacin
Sulpiride
Sunitinib
Tacrolimus
Tamoxifen
Telaprevir
Telavancin
Telithromycin
Terbutaline
Terfenadine
Tetrabenazine
Thioridazine
Tizanidine
Tolterodine
Toremifene
Trazodone
Trimethoprim-Sulfa
Trimipramine
Vandetanib
Vardenafil
Vemurafenib
Venlafaxine
Voriconazole
Vorinostat
Ziprasidone

5.4 Correlative studies

Before initiation of therapy with pracinostat (C4D1), after one cycle of pracinostat therapy (C5D1), after 3 cycles (C7D1), and then every 3 cycles (C10, C13, C16,...) while on the study, peripheral blood will be collected if possible for measurements of inflammatory cytokine levels, expression of different proteins related to intracellular

signaling, and methylation of genes. This will include collection of: one red top (10ml) and two purple top tubes (10ml each). Bone marrow aspirate will be collected every 6 cycles if possible (5ml purple top tube).

5.5 Pretreatment Evaluation

- History and physical exam including vital signs, body weight and height, and spleen and liver measurements. This also includes a transfusion history for 3 months prior to day 1 and concomitant medication notation (within 14 days of study day 1)
- CBC and differential, electrolytes (Na, K, Cl, Mg, HCO3), creatinine, uric acid, BUN, glucose, total and direct bilirubin, and SGPT, PT/PTT, INR (within 14 days of study day 1).
- Bone marrow biopsy and aspirate (within 1 month of study day 1, or within 3 months of study day 1 if patient was not on any therapy).
- ECG (within 14 days of study day 1)
- Pregnancy test (for FCBP only) within 7 days of study day 1
- Myeloproliferative Neoplasm Symptom Assessment Form Total Symptom Score (MPN-SAF TSS) questionnaire

5.6 Evaluation During Study

- Directed history and physical examination including vital signs, body weight, and spleen and liver measurements once each cycle on cycles 2-7, then once every 3 cycles (C10, C13, C16, ...). This also includes a transfusion history for previous cycle of therapy and concomitant medication notation. Spleen and liver measurements will be obtained by the physicians or physician assistants during the clinic visit and documented in the medical record.
- CBC and differential, electrolytes (Na, K, Cl, Mg, HCO3), creatinine, BUN, glucose, total bilirubin, and SGPT every 2 weeks for 6 cycles, then CBC with differential every cycle and electrolytes (Na, K, Cl, Mg, HCO3), creatinine, BUN, glucose, total bilirubin, and SGPT every 3 cycles and as deemed appropriate while on therapy. Therapy also includes the first 3 months of ruxolitinib alone.
- ECG will be performed prior to the first cycle of pracinostat (C4), then once during cycles 5 and 6, then every 3 cycles starting with cycle 10 (specifically, ECG should be performed approximately 90 minutes post pracinostat dosing on the day of visit to MD Anderson)
- Bone marrow aspiration and biopsy after cycles 6 (+/- 10 days) and 12 (+/- 10 days), and if deemed appropriate by the investigator, every 6 cycles after cycle 12.
- Response assessment after cycle 3 and cycle 6, then every 6 cycles. Assessment may not include bone marrow biopsy on all occasions.
- Collect any unused study drug and review patient study drug dosing diary for compliance during each cycle for the first 7 cycles then every 3 cycles.
- Continuous assessment of AEs
- Myeloproliferative Neoplasm Symptom Assessment Form Total Symptom Score (MPN-SAF TSS) questionnaire during each cycle for the first 7 cycles then every 3 cycles.

Every effort will be made to adhere to the schedule of events and all protocol requirements within the +/- 10 day window. Variations in schedule of events and other protocol requirements that do not affect the rights and safety of the patient will not be considered as deviations. Such variations may include laboratory assessments completed outside of schedule, occasional missed required research samples such as PK or PD. All dose adjustments will be made according to the protocol unless discussed with the PI and do not exceed the dosages described in the protocol.

Outside Physician Participation During Treatment

- MDACC Physician communication with the outside physician is required prior to the patient returning to the local physician. This will be documented in the patient record
- A letter to the local physician outlining the patient's participation in a clinical trial will request local physician agreement to supervise the patient's care
- Protocol required evaluations outside MDACC will be documented by telephone, fax or e-mail. Fax and/or e-mail will be dated and signed by the MDACC physician, indicating that they have reviewed it.
- Changes in drug dose and/or schedule must be discussed with and approved by the MDACC physician investigator, or their representative prior to initiation, and will be documented in the patient record.
- A copy of the informed consent, protocol abstract, and evaluation during treatment will be provided to the local physician.
- Documentation to be provided by the local physician will include drug administration records, progress notes, reports of protocol required laboratory and diagnostic studies and documentation of any hospitalizations.
- The home physician will be requested to report to the MDACC physician investigator all life threatening events within 24 hours of documented occurrence.
- Patients will return to MDACC each cycle for the first 6 cycles then every 3 cycles as long as on the study for evaluation.

The patient will be contacted by the PI and his staff 30 days after discontinuation of protocol +/-14 days to assess for AE's, unless the patient receives further MF-directed treatment.

